Study Objective: To evaluate the safety and efficacy of lebrikizumab compared with placebo in patients with moderate-to-severe AD	
FDA Endpoints	EMA Endpoints

Other Secondary Endpoints Specific for Maintenance Period:
 
 Percentage of patients from those re-randomized having achieved EASI-75 at Week 16 who continue to exhibit EASI-75 at Week 52 (EASI-75 calculated relative to baseline EASI score) Percentage of patients from those re-randomized having achieved IGA 0 or 1 and a ≥ 2-point improvement from Baseline at Week 16 who continue to exhibit an IGA 0 or 1 and a ≥ 2-point improvement from Baseline at Week 52 Time to loss of EASI-50 in the subset of patients who were re-randomized at Week 16 (EASI-50 calculated relative to baseline EASI score) Time to loss of EASI-75 in the subset of patients who were re-randomized and achieved EASI-75 at Week 16 (EASI-75 calculated relative to baseline EASI score) Time to loss of IGA response, i.e., developing an IGA score ≥ 2 with 2 points deterioration of achieved IGA response at Week 16, in the subset of patients who were re-randomized and achieved IGA 0 or 1 and a ≥ 2-point improvement from Baseline at Week 16 	
Major Secondary Endpoints Specific for Maintenance Period:
 
 Percentage of patients from those re-randomized having achieved EASI-75 at Week 16 who continue to exhibit EASI-75 at Week 52 (EASI-75 calculated relative to baseline EASI score) Percentage of patients from those re-randomized having achieved IGA 0 or 1 and a ≥ 2-point improvement from Baseline at Week 16 who continue to exhibit an IGA 0 or 1 and a ≥ 2-point improvement from Baseline at Week 52 Percentage of patients from those with a Pruritus NRS of ≥ 4-points at baseline re-randomized having achieved ≥ 4-point reduction from baseline at Week 16 who continue to exhibit ≥ 4-point reduction from baseline at Week 52 Percentage change in EASI score from Baseline at Week 52 in the subset of patients who were re-randomized at Week 16 
Other Secondary Endpoints Specific for Maintenance Period:
 
 Percentage change in SCORAD (having achieved EASI-75 at Week 16) from baseline at Week 52 Percentage of patients from those with a Pruritus NRS of ≥ 5-points at baseline re-randomized having achieved ≥ 4-point reduction from baseline at Week 16 who continue to exhibit ≥ 4-point reduction from baseline at Week 52 Time to loss of EASI-50 in the subset of patients who were re-randomized at Week 16 (EASI-50 calculated relative to baseline EASI score) Time to loss of EASI-75 in the subset of patients who were re-randomized and achieved EASI-75 at Week 16 (EASI-75 calculated relative to baseline EASI score) Time to loss of IGA response, i.e., developing an IGA score ≥ 2 with 2 points deterioration of achieved IGA response at Week 16, in the subset of patients who were re-randomized and achieved IGA 0 or 1 and a ≥ 2-point improvement from Baseline at Week 16

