5.1.3.2. Maintenance Escape Period

[figure not shown]
Patients who do not achieve an IGA of 0 or 1 or an EASI-75 at Week 16, patients received topical or systemic rescue therapy between baseline to Week 16 and those patients not maintaining an EASI-50 response following re-randomization at Week 24, 32, 40, or 48 will be

assigned to an Escape Arm and receive lebrikizumab 250 mg as open-label treatment Q2W through Week 52. Patients not achieving an EASI-50 response in the Escape Arm after 8 weeks of treatment will be terminated from the study.

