6.1. General Considerations

Statistical analysis of this study will be the responsibility of Eli Lilly and Company (Lilly). The latest version of the Medical Dictionary for Regulatory Activities (MedDRA) will be used.

Analyses and summaries from assessment of endpoints described in the protocol (for example, described in KGAB Protocol Table 1) are planned to be included in a clinical study report (CSR). Analyses and summaries for key safety data are also planned to be included in the CSR. Results from additional efficacy analysis and other safety analyses may also be provided in the CSR as deemed appropriate.

Any change to the data analysis methods described in the protocol will require a protocol amendment ONLY if it changes a principal feature of the protocol. Any other change to the data analysis methods described in the protocol and the justification for making the change will be described in the CSR.

All statistical processing will be performed using SAS® unless otherwise stated. Some of the analyses described in this document will be incorporated into interactive display tools instead of or in addition to static displays. Except where noted, all statistical tests will be two-sided and will be performed at the 0.05 level of significance.

The Schedule of Visits and Procedures outlined in the protocol specifies the allowable windows for assessments. Assessments performed outside these windows will not be excluded from any analysis, unless specified otherwise.

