6.1.3. General Considerations for Analyses During Maintenance Period

Maintenance Period starts at the first injection of study treatment at Week 16 and ends on the date of Week 52 or the ETV (between Weeks 16 and 52) unless specified otherwise.

For the efficacy and health outcome analyses, baseline is defined as the last available value before the first injection in Induction Period and, in most cases, will be the value recorded at Baseline Visit (Day 1).

Unless otherwise specified, efficacy and health outcome scores at Week 16 prior to entering Maintenance Period will be presented for the visitwise reports for Maintenance Period.

Unless specified otherwise, for the safety analyses during Maintenance Period, baseline is defined as the last available value before first injection in Maintenance Period. In most cases, this will be the measure recorded at Week 16. For TEAEs, baseline is the events ongoing just prior to the first injection of the study drug injection at Week 16.

For patients in the Maintenance Primary and Secondary Population who met escape criteria (EASI-50 nonresponse) and escaped to lebrikizumab 250 mg Q2W at Weeks 24, 32, 40 and 48, only data in the Maintenance blinded period (up to the time of escape) will be included in both efficacy and safety analyses.

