6.2.2.1. Maintenance Primary Estimand (Hybrid)

The maintenance primary estimand is a hybrid estimand representing the clinical question of interest: what is the difference between treatment conditions, i.e., Lebrikizumab vs Placebo, in the target patient population, in successful responses or means after 52 weeks achieved without use of systemic rescue medication, without transferring to escape arm, if topical rescue medication were not available and if all patients continued with treatment except those who discontinued due to lack of efficacy?

The maintenance primary estimand is described by the following attributes:

- A. Population: Maintenance Primary Population as described in Section 6.1.1.
- B. Endpoint: apply to all major and other secondary endpoints for Maintenance Period
- C. How to account for intercurrent events (ICEs)
 - a. Subjects who require any use of systemic rescue medication, discontinue treatment due to lack of efficacy after week 16, or transfer to escape arm will be considered as treatment failures, i.e., non-responder, after the ICEs. Therefore, composite strategy is used for these types of ICEs.
 - b. For subjects who require any use of topical rescue medication, a hypothetical strategy will be used to estimate what the treatment effect would have been if

subjects continued with treatment. Therefore, hypothetical strategy is used for these types of ICEs.

- c. For subjects who discontinue treatment due to reasons other than lack of efficacy after week 16, a hypothetical strategy will be used to estimate what the treatment effect would have been if subjects continued with treatment. Therefore, hypothetical strategy is used for these types of ICEs.

D. Population-level summary: difference in response proportions or means between treatment conditions

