6.2.2.2. Maintenance Supportive Estimand (Hybrid)

The maintenance supportive estimand for both continuous and categorical endpoints is a hybrid estimand representing the clinical question of interest: what is the difference between treatment conditions, i.e., Lebrikizumab vs Placebo, in the target patient population, in successful responses or means after 52 weeks achieved without use of systemic rescue medication, without transferring to escape arm, regardless of use of topical rescue medication and if all patients continued with treatment except those who discontinued due to lack of efficacy?

The maintenance primary estimand is described by the following attributes:

- A. Population: Maintenance Primary Population as described in Section 6.1.1.
- B. Endpoint: apply to all major and other secondary endpoints for Maintenance Period
- C. How to account for intercurrent events (ICEs)
 - a. Subjects who require any use of systemic rescue medication, discontinue treatment due to lack of efficacy after week 16, or transfer to escape arm will be considered as treatment failures, i.e., non-responder, after the ICEs. Therefore, composite strategy is used for these types of ICEs.
 - b. For subjects who require any use of topical rescue medication, observed data will be used. Therefore, treatment policy strategy is used for these types of ICEs.
 - c. For subjects who discontinue treatment due to reasons other than lack of efficacy after week 16, a hypothetical strategy will be used to estimate what the treatment effect would have been if subjects continued with treatment. Therefore, hypothetical strategy is used for these types of ICEs.
- D. Population-level summary: difference in response proportions or means between treatment conditions

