6.4.2.3. Maintenance Period LOCF

Maintenance LOCF will be used to handle missing data relative to maintenance supportive estimands for continuous endpoints (Hypothetical). In this analysis, the values subsequent to rescue medication use (per Protocol Section 6.3), treatment discontinuation or transfer to escape arm will be made missing. All missing values will be imputed using LOCF. Baseline value will be used for imputation if there is no postbaseline observation.

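### Week 52 SCORAD percentage change is compared between arms only with LOCF, which carries the Week 16 responder score for rescued or escaped patients and departs from the SAP's own hybrid-estimand scope

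*SAP*

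**What the plan says.** - **Endpoint.** SAP Table KGAB.4.1 lists, under EMA other secondary endpoints for maintenance, "Percentage change in SCORAD (having achieved EASI-75 at Week 16) from baseline at Week 52". Protocol Table 1 has the same endpoint in its EMA column. SAP 6.1 commits to reporting it: "Analyses and summaries from assessment of endpoints described in the protocol (for example, described in KGAB Protocol Table 1) are planned to be included" in the study report.
- **Analysis.** Table KGAB.6.12 gives it one row: maintenance supportive (hypothetical) estimand, ANCOVA with LOCF. Table KGAB.6.9 agrees, since SCORAD falls among the remaining continuous endpoints. SAP 6.1.3.1 adds descriptive statistics by arm but no other comparison.
- **LOCF rule (SAP 6.4.2.3).** For values after rescue medication, "treatment discontinuation or transfer to escape arm will be made missing. All missing values will be imputed using LOCF".
- **Escape.** SAP 5.1.3.2 sends to the Escape Arm "those patients not maintaining an EASI-50 response following re-randomization at Week 24, 32, 40, or 48". SAP 6.1.3 adds that for escaped patients "only data in the Maintenance blinded period (up to the time of escape) will be included in both efficacy and safety analyses".
- **Baseline.** For maintenance efficacy, "baseline is defined as the last available value before the first injection in Induction Period" (SAP 6.1.3).
- **Estimand scope.** The maintenance primary hybrid estimand states: "Endpoint: apply to all major and other secondary endpoints for Maintenance Period". The supportive hybrid (SAP 6.2.2.2) has the same scope and differs on topical rescue: "For subjects who require any use of topical rescue medication, observed data will be used".
- **Schedule.** Protocol 7.10, 7.19, 7.20 and Appendix 1 Table 7 collect SCORAD at Week 16 and at Week 52 or early termination. Protocol 7.11 to 7.18 (Weeks 20 to 48) and 7.22 (unscheduled visits for exacerbation) list IGA, BSA and EASI only.

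**The concern.** LOCF needs an observation close to the event to say anything about the patient's state when treatment failed. SCORAD has none during maintenance. Once values after rescue or escape are deleted, the last scheduled score left was taken before the first maintenance injection, when the patient qualified as a responder. A relapse that the protocol itself recognises, and acts on by moving the patient to the Escape Arm, leaves no trace in the SCORAD comparison.

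The SAP also disagrees with itself. The scope lines of 6.2.2.1 and 6.2.2.2 cover this endpoint, so escape, systemic rescue and lack-of-efficacy discontinuation should be set to baseline (Table KGAB.6.4). The analysis tables assign it neither hybrid. EASI percentage change, by contrast, gets both, with LOCF as supplementary.

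At stake is how the arm means are read. They would be taken as durability of SCORAD response on each maintenance regimen and after withdrawal to placebo.

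**Working it through.** **1. Which score is carried.** Post-baseline SCORAD is scheduled at Week 16 and at Week 52 or early termination. Baseline is pre-induction, so Week 16 counts as post-baseline. Deleting everything after rescue or escape leaves Week 16, and LOCF places it at Week 52. A patient with no Week 16 SCORAD would get the Day 1 value instead. Someone who discontinues without rescue or escape has an early-termination SCORAD; that case is not part of this point.

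**2. Gap that follows from the rules alone.**
- Subset entry: EASI improvement of at least 75% at Week 16.
- Escape: EASI improvement below 50%.
- EASI loss by the escape visit: more than 75 − 50 = 25 percentage points.
- SCORAD loss under LOCF for the same patient: 0.

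Without earlier rescue, LOCF of EASI carries the escape-visit value (improvement below 50%). The same rule therefore records the relapse on EASI and misses it on SCORAD.

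**3. Arm sizes.** The plan gives no precision or power figure for SCORAD. Its only such figure, more than 95% power with 96 versus 48 patients, reproduces: the continuity-corrected test gives 95.2% for IGA and 99.6% for EASI-75. Taking the 48% EASI-75 rate from SAP 5.2: 400 × 2/3 × 0.48 = 128 responders. Re-randomised 2:2:1, that is 51.2, 51.2 and 25.6, or about 51, 51 and 26.

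**4. Illustration; every SCORAD input is assumed.** Let f be the share of an arm with escape or systemic rescue: 0.30 to 0.50 on placebo (fP), 0.10 to 0.20 on active (fA). Let W be the mean Week 16 change, −70% to −80%, held by patients without an event. Let L be what failing patients would show at Week 52 on their re-randomised treatment, −20% to −45%. Results are percentage points of SCORAD change.

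| Quantity | Formula | Range |
|---|---|---|
| Failing patients' contribution to the arm difference, LOCF | (fP − fA) × (W − W) | 0 |
| Same, primary hybrid (set to baseline) | (fP − fA) × (0 − W) | 0.10 × 70 = 7 to 0.40 × 80 = 32 |
| Same, hypothetical target of 6.2.2.4 | (fP − fA) × (L − W) | 0.10 × 25 = 2.5 to 0.40 × 60 = 24 |
| LOCF error in the placebo mean, for 6.2.2.4 | fP × (L − W) | 0.30 × 25 = 7.5 to 0.50 × 60 = 30 |
| LOCF error in an active mean, for 6.2.2.4 | fA × (L − W) | 0.10 × 25 = 2.5 to 0.20 × 60 = 12 |
| LOCF versus hybrid, placebo mean | fP × \|W\| | 0.30 × 70 = 21 to 0.50 × 80 = 40 |

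The last row is a difference between two estimands, not an error of LOCF. With equal failure rates the arm difference is unaffected and only the arm means shift.

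**5. Precision.** Assume a residual SD of 15 to 25 points.
- LOCF: SE = SD × √(1/26 + 1/51) = 3.61 to 6.02; 95% half-width 7.1 to 11.8.
- Hybrid: arm variance = (1 − f) × SD² + f(1 − f) × W². SE = 7.63 to 10.17; half-width 15.0 to 19.9.
- Ratio of half-widths: 1.45 to 2.62.

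The hybrid figures omit between-imputation variance, so they are on the low side.

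**6. Size of the imputation model.** A multivariate normal model in k variables has k + k(k+1)/2 parameters. Three SCORAD times plus one EASI visit: k = 4, 14 parameters. Three SCORAD times plus all nine EASI visits from Week 20 to Week 52: k = 12, 90 parameters, against about 26 patients in the placebo arm.

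**The case against.** The best defence is that the endpoint-specific tables govern. SAP 6.2.2.4 sends the reader to 6.4.2 and 6.11 for detail, Tables KGAB.6.9 and KGAB.6.12 agree with each other, and only a general scope line differs. Narrowing that line would remove the inconsistency. This stands: the text alone does not settle which side prevails. It would not cure the carried Week 16 score.

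A second defence is that induction uses LOCF in the same way for endpoints collected once post-baseline (Table KGAB.6.6). The effect is opposite. In induction a rescued patient has no earlier post-baseline SCORAD, so SAP 6.4.1.4 carries the baseline value. In maintenance the rule carries a responder value.

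Third, relapse is visible elsewhere: EASI percentage change under both hybrids, time to loss of EASI-50 and EASI-75, SCORAD75 and SCORAD90 with NRI, counts entering escape, and percentage rescued by visit. This stands and limits the severity. None of these is the SCORAD mean.

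Fourth, EQ-5D and PROMIS share the Week 16 and Week 52 schedule and the same LOCF rule. The case for treating SCORAD differently is its listing as a Week 52 maintenance endpoint in Protocol Table 1. That is a reason for priority, not a difference in method.

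Fifth, the primary hybrid sets scores after topical rescue to missing, so those patients still lean on Day 1 and Week 16 SCORAD. This also stands, and is why the supportive hybrid is needed.

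**Conclusion.** The point holds as a minor-to-moderate correction. From the documents alone, a patient rescued or escaped in maintenance enters the only comparative analysis of this endpoint with a score that holds no on-maintenance information, and an escaper who has lost more than 25 points of EASI improvement is recorded as unchanged. The analysis tables also do not match the stated scope of the hybrid estimands. Arm-level durability is overstated wherever relapse occurs. The bias of the arm difference toward zero rests on relapse being commoner on placebo, which is an assumption.

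A reader might infer more than the documents support:

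- **A false efficacy claim or lost error control.** The endpoint is not major and lies outside the EMA hierarchy in SAP 6.6.2; under the assumption above the bias runs against the drug.
- **No other SCORAD mean will be seen.** SAP 6.1.3.1 plans descriptive means, though it names neither the EASI-75 subset nor an imputation rule.
- **The Week 16 score is worthless.** It is a usable predictor of Week 52; the fault is using it as the Week 52 value.
- **Table KGAB.6.10 assigns LOCF to SCORAD.** It is a seed table and simply has no SCORAD entry.
- **LOCF is wrong by 21 to 40 points.** That range compares two estimands on assumed inputs.

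**What to change.** 1. Make the maintenance primary hybrid estimand of Table KGAB.6.4 the main analysis of Week 52 SCORAD percentage change: escape, systemic rescue and lack-of-efficacy discontinuation set to baseline, MCMC-MI for the rest. Use a sparse imputation model of Day 1, Week 16 and Week 52 SCORAD, plus at most one on-maintenance EASI visit named in advance.
2. Add the supportive hybrid of 6.2.2.2, which keeps observed Week 52 scores after topical rescue. Protocol 6.3 permits intermittent topical use in maintenance, and both LOCF and the primary hybrid discard those scores.
3. Relabel LOCF as supplementary, and state in 6.4.2.3 that for SCORAD the value carried after rescue or escape is Week 16.
4. Align Tables KGAB.6.9, KGAB.6.10 (add a SCORAD seed) and KGAB.6.12.
5. For the other remaining continuous endpoints, reconcile the word *all* in 6.2.2.1 and 6.2.2.2 with the tables; no new imputation is needed there.

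The cost is SAP wording, one extra imputation program and a seed, with no new data or visits. Intervals widen, by about 1.45 to 2.6 times in the illustration, because relapsed patients now differ from maintained ones. The change belongs before maintenance treatment is unblinded; if that has happened, the added analyses should be labelled post hoc.

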6.5. Multicenter Studies

This study will be conducted by multiple investigators at multiple sites internationally. Typically, a logistic regression with treatment, site, and treatment-by-site may be used to assess the consistence of treatment effect in sites. However, due to a large number of sites and countries and relative small sample size in the study, this logistic regression model will not likely converge. The site will not be adjusted as a covariate. Instead, the subgroup analysis on the region will be evaluated. The countries will be categorized into geographic regions as in Section 6.3. Subgroup analysis details are provided in Section 6.15.1.

For the analysis of the primary endpoint, the presence of a treatment-by-geographic region interaction will be tested at 10% significance level. Treatment group comparisons for the primary endpoint will be presented separately for each geographic region. When there is evidence of an interaction ($p < .10$), descriptive statistics may be used to assess whether the interaction is quantitative (that is, the treatment effect is consistent in direction but not size of effect) or qualitative (the treatment is beneficial for some but not other geographic regions or countries).

6.6. Multiple Comparisons/Multiplicity

6.6.1. Multiplicity Control for FDA

A prespecified graphical multiple testing approach (Bretz et al. 2009, 2011) will be implemented to control the overall Type I error rate at two-sided alpha of 0.05, for all primary and major secondary endpoints for FDA. Multiple testing adjusted p-values using “Algorithm 2” described by Bretz et al. (2009) will be calculated, and any hypothesis tests with a multiple testing adjusted p-value of less than 0.05 will be considered statistically significant. This graphical approach is a closed testing procedure; hence, it strongly controls the family-wise error rate across all endpoints (Bretz et al. 2009, 2011; Alosch et al. 2014). Each hypothesis is represented as a node in a graph. Directed arrows between the nodes with associated weights represent how alpha is passed from its initial allocation to other nodes.

The following is a list of primary and major secondary endpoints to be tested for FDA.

Primary endpoint:

- [IGA01 W16] Percentage of patients with an Investigator Global Assessment (IGA) score of 0 or 1 and a reduction ≥ 2 points from Baseline to Week 16.

Major secondary endpoints:

- [EASI-75 W16] Percentage of patients achieving EASI-75 ($\geq 75\%$ reduction from Baseline in Eczema Area and Severity Index [EASI] score) at Week 16.
- [EASI-90 W16] Percentage of patients achieving EASI-90 ($\geq 90\%$ reduction from Baseline in EASI score) at Week 16.
- [Pruritus NRS-4 W16] Percentage of patients with a Pruritus Numerical Rating Scale (NRS) of ≥ 4 -points at Baseline who achieve a ≥ 4 -point reduction from Baseline to Week 16.
- [Pruritus NRS-4 W4] Percentage of patients with a Pruritus NRS of ≥ 4 -points at Baseline who achieve a ≥ 4 -point reduction from Baseline to Week 4.
- [Pruritus NRS-4 W2] Percentage of patients with a Pruritus NRS of ≥ 4 -points at Baseline who achieve a ≥ 4 -point reduction from Baseline to Week 2.
- [IGA01 W4] Percentage of patients with an IGA score of 0 or 1 and a reduction ≥ 2 points at Week 4.

- [IGA01 Adult W16] Percentage of patients with an IGA score of 0 or 1 and a reduction ≥ 2 points at Week 16 in adults.
- [Sleep loss W16] Percentage of patients with a Sleep-loss score ≥ 2 points at Baseline who achieve a ≥ 2 points reduction from Baseline at Week 16.

Figure KGAB.6.2 describes the graphical testing scheme for FDA.

[figure not shown]

Figure KGAB.6.2. Graphical approach to control type 1 error rate for Study J2T-DM-KGAB for FDA purposes.

